16.2.3 Time to Symptomatic Progression (TTSP)

TTSP will be measured as the time (in months) from the date of first trial treatment administration to the date of deterioration of symptoms assessed by FHSI-8 (defined as at least a 4-point decrease, i.e., lower score, compared with baseline value), or deterioration to ECOG performance score 4, or death. TTSP will be censored at the last FHSI-8 or ECOG assessment with a non-missing value as of the data cut-off date for subjects that do not experience symptomatic progression. Subjects that are missing a baseline FHSI-8 assessment and all post-baseline ECOG assessments will be censored at the first date of trial treatment administration. The FHSI-8 will be scored using the scoring guidelines (version 4.0) shown in Appendix 2.

The date of event/censoring is defined as follows:

Status Censoring		Date of event / censoring
Progressed	Event	Earliest date corresponding to deterioration of symptoms (decrease of 4 in FHSI-8 score from baseline, ECOG performance score of 4, or death)
Didn't progress	Censored	Latest date from last FHSI-8 assessment, ECOG assessment, or date of first study drug administration

TTSP (months) = (date of deterioration of symptoms/censoring – date of first trial treatment administration + 1)/30.4375

The analysis of TTSP will be performed using Kaplan-Meier methods with the same approach for PFS described in Section 16.2.1.

16.2.4 Overall Survival (OS) Time

OS time is defined as the time (in months) from the date of first treatment administration to the date of death due to any cause.

The date of event/censoring is defined as follows:

Survival Status	Source Censoring		Date of event/censoring
Died	Death eCRF	Event	Date of death
Alive as of the data cutoff date (no date of death)	To be determined as defined in Section 11	Censored	Last date known to be alive (defined in Section 11)

OS (months) = $\frac{\text{date of death/censoring} - \text{date of first trial treatment administration} + 1)/30.4375$

The analysis of OS will be performed using Kaplan-Meier methods with the same approach for PFS described in Section 16.2.1 and will be repeated for the subgroups described in Section 10. In addition, the pattern of censoring will be summarized (e.g. censoring due to death, study withdrawal, lost to follow-up, censoring due to data cut-off).

16.2.5 Best Overall Response (BOR)

The confirmed best overall response (BOR) is the best response recorded from the start of treatment until PD. The BOR across all time points will be established applying the confirmation criteria based separately on RECIST 1.1 and mRECIST, taking confirmation requirements into account as presented in Table 1. Subjects that do not have measureable disease at baseline may have a BOR of Non-CR/non-PD. This is determined by using Non-CR/non-PD in place of SD in Table 1. CR/PR may be claimed only if the corresponding criteria in Table 1 are met at a subsequent time point. The time gap of two consecutive tumor response evaluations is the difference of two dates (i.e. the earliest scan date of target lesions associated with each assessment visit). SD may be claimed only if the SD criteria are met at least once after first administration at a minimum interval of 42 days. The time interval for SD will be calculated as (date of overall response - first dosing date of trial drug +1). The confirmation of response must not necessarily be at the next scan, but could be at any subsequent scan before PD. For instance, if a subject has PR-SD-PR or PR-not evaluable (NE)-PR at consecutive tumor assessments, the BOR would qualify for PR. The number and percentage of subjects with BOR of CR, PR, SD, PD, Non-CR/non-PD and NE will be summarized once for BOR per investigator as assessed by RECIST 1.1 and again for BOR per investigator as assessed by mRECIST.

Tumor response data will be presented in a listing.

A figure displaying the BOR for each subject along with their percent change from baseline in AFP value will be displayed against time (weeks) in a line plot by the following baseline categories: < 200 ug/L, >= 200 ug/L, < 400 ug/L, and >= 400 ug/L. The BOR for each subject per investigator as assessed by RECIST 1.1 will be indicated in the figure.

A swimmer plot summarizing exposure information and response data will be presented by c-Met status (IHC/ISH). The BOR for each subject per investigator as assessed by RECIST 1.1 will be indicated in the figure. Another identical swimmer plot will be created, but it will display the BOR for each subject per investigator as assessed by mRECIST.

Table 1 – Best Overall Response when Confirmation of CR and PR is Required

Overall response response Subsequent time

First time point point Best overall response

CR	CR	CR
CR	PR	SD, PD or PR ^a
CR	SD	SD provided minimum criteria for SD duration met, otherwise PD
CR	PD	SD provided minimum criteria for SD duration met, otherwise PD
CR	NE	SD provided minimum criteria for SD duration met, otherwise NE
PR	CR	PR
PR	PR	PR
PR	SD	SD provided minimum criteria for SD duration met, otherwise NE
PR	PD	SD provided minimum criteria for SD duration met, otherwise PD
PR	NE	SD provided minimum criteria for SD duration met, otherwise NE

CR = complete response, PR = partial response, SD = stable disease, PD = progressive disease, and NE = not evaluable.

Objective tumor response

Objective tumor response will be evaluated by the objective response rate (ORR). The ORR is the proportion of subjects having achieved a BOR of CR or PR. The ORR will be established applying the criteria based on the investigator's assessment using RECIST 1.1. Subjects with a BOR of Non-CR/non-PD (possible only for subjects without measurable disease at baseline) are not considered as having achieved objective response. Therefore these subjects will be counted in the denominator of the rate but not the numerator.

ORR will be summarized along with corresponding two-sided exact Clopper-Pearson (2) 90% CIs.

The above analyses will be repeated using the ORR established by applying the criteria based on the investigator's assessment using mRECIST.

Disease Control

^a If a CR is truly met at first time point, then any disease seen at a subsequent time point, even disease meeting PR criteria relative to baseline, makes the disease PD at that point (since disease must have reappeared after CR). Best response would depend whether minimum duration for SD was met. However, sometimes CR may be claimed when subsequent scans suggest small lesions were likely still present and in fact the subject had PR, not CR at the first time point. Under these circumstances, the original CR should be changed to PR and the best response is PR.

Disease control will be evaluated by the disease control rate, defined as the proportion of subjects having achieved a BOR, per investigator as assessed by RECIST 1.1, of CR, PR, or SD. In case SD is the BOR, SD must be observed at a minimum interval of 42 days after the first dose of study drug. Subjects with a BOR of Non-CR/non-PD (possible only for subjects without measurable disease at baseline) are not considered as having achieved a BOR of CR, PR, or SD. Therefore, these subjects will be counted in the denominator of the rate but not the numerator.

Disease control rate will be summarized along with corresponding two-sided exact Clopper-Pearson (2) 90% CIs.

The above analyses will be repeated using disease control rate defined as the proportion of subjects having achieved a BOR, per investigator as assessed by mRECIST of CR, PR, or SD. SD must be observed at the end of Cycle 2 or later.

Tumor assessments will also be assessed using an 18F-fluoro-D-glucose (FDG) positron emission tomography (PET) scan. All FDG-PET results will be presented in a data listing using data collected from the "Tumor Assessment Using 18F-Fluoro-D-Glucose (FDG) Positron Emission Tomography (PET)" eCRF page.

16.2.6 Duration of Response

The duration of response will be calculated for each subject with a response of CR or PR according to RECIST 1.1 and mRECIST as the time from first observation of response until first observation of documented disease progression or death when death occurs within 12 weeks of the last tumor assessment. For subjects with a response of CR or PR but neither documented disease progression nor death within 12 weeks after the last tumor assessment, the duration of response will be censored at the date of the last adequate tumor assessment.

Duration of response (weeks) = (date of PD or death – date of CR or PR + 1) / 7

Duration of response information will be included on the tumor response listing.

16.2.7 Biological Response

Biological response is defined as the proportion of subjects with a decrease in AFP level of more than 20% at the Cycle 3 assessment, or the last assessment for subjects that terminated treatment prior to the Cycle 3 assessment, as compared with baseline. AFP level is measured at screening, Cycle 1 Day 1 (only if the screening measurement was done more than 7 days prior), Day 1 of every cycle thereafter for which there is a visit, and the End of Treatment visit.

Biological response will be summarized, including corresponding two-sided exact Clopper-Pearson (2) 90% CIs.

If sufficient HGF data is available, scatter plots of best (minimum) on treatment AFP value versus both baseline HGF (CAF and cytoplasmic) will be provided.

Biological response will be flagged on the tumor marker listing. (See Section 17.3.)

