### 8.1 Sample Size

For Phase Ib, the sample size of up to 18 subjects was not based on any statistical assumptions; rather, it follows the "3+3 rule," a well-established current methodology in the design of dose-finding trials in oncology.

For Phase II, the sample size of 48 subjects was determined as follows. Under the assumption of no treatment effect, the rate of MET+ subjects without progression at 12 weeks (the primary endpoint) was assumed to be ~15% based on historical data. It is expected that MSC2156119J treatment will lead to 30% MET+ subjects without progression at 12 weeks. The null hypothesis (that the true rate of subjects without progression at 12 weeks is  $\leq 15\%$ ) will be tested using a one-stage design based on the exact binomial distribution (5). With a type I error rate of 5% (one-sided) if the true rate of subjects without progression at 12 weeks is  $\leq 15\%$ , to reach a power of 80% if the true rate of subjects without progression at 12 weeks is 30%, this design requires 48 subjects to be treated in Phase II.

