#### 8.3.2 Secondary Endpoints

#### 8.3.2.1 Efficacy Endpoints

Secondary endpoints are as follows:

• TTP, measured as the time (in months) from the date of first study drug administration to the date of radiological confirmation of PD performed according to RECIST Version 1.1. In HCC, TTP is recommended as a sensitive endpoint in measuring antitumor activity of molecularly targeted agents in HCC Phase II trials since it is less vulnerable to the potential confounding effect of underlying liver disease than the traditional endpoint PFS. For this reason, TTP will be regarded as the major sensitivity analysis for the primary endpoint of PFS status.

- PFS, defined as the time (in months) from first study drug administration to either first observation of PD (as assessed by RECIST Version 1.1) or occurrence of death due to any cause within 12 weeks of the last tumor assessment, whichever occurs first.
- PFS, defined as the time (in months) from first study drug administration to either first observation of PD (as assessed by mRECIST for HCC) or occurrence of death due to any cause within 12 weeks of the last tumor assessment, whichever occurs first.
- Time-to-symptomatic progression (TTSP) as subject-reported outcome, defined as the time (in months) from first study drug administration to the date of deterioration of symptoms assessed by FHSI-8 (defined as at least a 4-point increase, i.e., higher score, compared with baseline value), or deterioration to ECOG performance score 4, or death (applicable for Phase II only).
- OS time, defined as the time (in months) from first study drug administration to the date of death.
- Objective tumor response: Subjects with best overall tumor assessment of CR or partial response according to RECIST Version 1.1 from first study drug administration until first occurrence of PD.
- Disease control: Subjects with best overall tumor assessment of CR, partial response, or SD according to RECIST Version 1.1 from first study drug administration until first occurrence of PD. SD must be observed at the end of Cycle 2 or later.
- Biological response as measured by serum AFP, defined as a > 20% decrease in AFP level by Cycle 2 compared with baseline.

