17.3 Clinical Laboratory Evaluation

Laboratory results are assessed at a local laboratory and will be classified using NCI-CTCAE Version 4.0. Values that are below the limit of detection will be imputed as half of the detection limit.

The following will be presented:

- Tables with descriptive statistics and boxplots for both chemistry and hematology values and their changes from baseline by visit
- An eDISH (evaluation of drug-induced serious hepatotoxicity) plot for total bilirubin and ALT
- For NCI-CTCAE gradable chemistry and hematology parameters:
 - O Tables for the worst grade (≥ 0 , ≥ 3 , or ≥ 4) during the on-treatment period using counts and percentages by laboratory parameter
 - Tables showing shifts from baseline to highest (worst) on-treatment grade (0, 1, 2, 3, or 4) For those parameters which are graded for increase as well as decrease such as potassium (hypokalemia/hyperkalemia), the toxicities will be summarized separately.
- For non NCI-CTCAE gradable chemistry and hematology parameters:
 - Tables displaying shifts from baseline to abnormal values for the maximum and minimum post-baseline values based on reference range (Low, Normal, or High)

The following hematology parameters were collected:

- Hemoglobin
- Hematocrit
- Red blood cell count
- White blood cell count
- Differential WBC
- Platelet count

The following chemistry parameters were collected:

- Blood urea nitrogen (BUN)
- Urea
- Creatinine
- AST
- ALT
- Gamma-glutamyl transpeptidase (GGT)
- Total bilirubin
- Direct bilirubin (if total is abnormal)
- Lipase
- Amylase
- Total Protein
- Albumin
- Alkaline Phosphatase
- Creatinine Clearance
- Sodium
- Potassium
- Calcium
- Magnesium
- Glucose

The following laboratory parameters collected on the eCRF will be listed in dedicated listings presenting all corresponding collected information:

- Coagulation: prothrombin time, activated partial thromboplastin time (aPTT), and International Normalized Ratio (INR)
- Pregnancy Tests: serum and urine
- Urinalysis: glucose, ketones, blood, pH, proteins, nitrites, leukocytes, red blood cell count, white blood cell count

- HBV panel and anti-HCV (hepatitis C virus) antibodies: HBsAg (hepatitis B surface antigen), HBeAg (hepatitis B e antigen), anti-HBc (anti-hepatitis B core antigen), and anti-HCV
- Viral load of HBV/HCV (only for subjects with hepatitis B at screening)
- Tumor markers: serum AFP

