Under the assumption of no treatment effect, the rate of MET+ subjects without progression at 12 weeks was assumed to be ~15% based on historical data. It is expected that tepotinib treatment will lead to 30% MET+ subjects without progression at 12 weeks. The null hypothesis that the true rate of subjects without progression at 12 weeks is \leq 15% will be tested using a one-stage design based on the exact binomial distribution. With a type I error rate of 5% (one-sided) if the true rate of subjects without progression at 12 weeks is \leq 15%, to reach a power of 80% if the true rate of subjects without progression at 12 weeks is 30%, this design requires 48 subjects to be treated in Phase II.

Randomization is not applicable.

8 Overview of Planned Analyses

This SAP covers the analyses for efficacy and safety for the final analysis. Statistical analyses will be performed using cleaned electronic Case Report Form (eCRF) data. An administrative interim efficacy analysis, described in a separate analysis plan, was previously performed. Further administrative interim analyses at time points that are not specified in the protocol may be performed for internal planning purposes.

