10.2 Definition of Analysis Sets and Subgroups

Screening Analysis Set

The Screening Analysis Set includes all subjects who signed the Informed Consent Form (ICF). The Screening Analysis Set will be used for the display of disposition data. Rescreened subjects will be counted once in the Screening Analysis Set. For subjects who are rescreened, the most recent data will be presented in listings.

Intent-to-Treat/Safety Analysis Set

The ITT/SAF Analysis Set includes all subjects who have been administered at least one dose of tepotinib. The ITT/SAF Analysis Set will be used for all safety and efficacy analyses.

₹\//

The below subgroup analyses may be performed on the primary endpoint and some secondary endpoints. The subgroup analyses are exploratory in nature. The following subgroups will be defined:

- Age: < 65 years versus ≥ 65 years
- Gender: male versus female
- Country
- Baseline ECOG: 0 versus 1
- Vascular invasion and/or extrahepatic spread: presence versus absence
- Underlying disease or medical condition related to etiology: HCV versus other
- AFP elevation at baseline: ≥ 200 IU/mL versus < 200 IU/mL
- Prior local-regional therapy: yes versus no
- Baseline c-Met Status: Immunohistochemistry (IHC): IHC 0, IHC 1+, IHC 2+, IHC3+
- Baseline c-Met Status: In Situ Hybridization (ISH): ISH+, ISH-
- Baseline Cancer-Associated Fibroblast (CAF) HGF: above the median, below/at the median, not done, not evaluable.
- Baseline Cytoplasmic HGF: above the median, below/at the median, not done, not evaluable
- Baseline Circulating HGF
 - o Above the median, below/at the median, not done, not evaluable
 - Above upper quartile (25% quantile), below/at upper quartile, not done, not evaluable
- Baseline Shedded c-Met
 - O Above the median, below/at the median, not done, not evaluable
 - o Above upper quartile, below/at upper quartile, not done, not evaluable
- Baseline IL-8
 - O Above the median, below/at the median, not done, not evaluable
 - Above upper quartile, below/at upper quartile, not done, not evaluable
- Baseline c-Met Amplification (ISH): c-Met amplification +, c-Met amplification –
- Baseline HCV Status: HCV versus non-HCV
- Baseline HBV Status: HBV versus non-HBV

Baseline HBV/HCV Status: HBV or HCV versus neither HBV nor HCV

Analyses	Screening Analysis Set	ITT/SAF Analysis Set	
Disposition	✓		
Demographics		✓	
Baseline Assessments		✓	
Past and Concomitant Therapies		✓	
Compliance and Exposure		✓	
Primary		✓	
Secondary		✓	
CCI			
CCI			
CCI			

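### AFP response is counted over all treated subjects with no baseline AFP condition, and no planned table gives the rate among subjects whose AFP was raised at baseline

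*SAP*

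**What the plan says.** Protocol 8.3.2.1 lists the secondary endpoint as "Biological response as measured by serum AFP, defined as a > 20% decrease in AFP level by Cycle 2 compared with baseline". Phase II SAP 16.2.7 moves the time point, a change declared in its section 9: "Biological response is defined as the proportion of subjects with a decrease in AFP level of more than 20% at the Cycle 3 assessment". Where a subject stopped treatment earlier, the final available reading is used instead. Phase Ib SAP 16.2.1.6 uses the same definition. None of these texts sets a minimum baseline AFP.

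The analysis set for secondary endpoints is ITT/SAF, meaning everyone given at least one dose. Section 11 of each SAP takes percentages over the analysis set unless otherwise specified. None of the 11 inclusion and 22 exclusion criteria in Protocol 5.3 mentions AFP. Phase II SAP 10.2 defines a subgroup split, "AFP elevation at baseline: ≥ 200 IU/mL versus < 200 IU/mL", so subjects below that level are expected.

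Four other provisions bear on the point:
- Phase II SAP 16.3 names the primary endpoint, PFS and OS for subgroup presentation. AFP response is not among them.
- Phase II SAP 16.2.5 and Phase Ib SAP 16.2.1.4 plan a line plot of percent change in AFP by baseline category, cut at 200 and 400 µg/L.
- Biological responders are flagged on the tumour marker listing.
- Phase Ib SAP 17.3 has a rule for low readings: "Values that are below the limit of detection will be imputed as half of the detection limit". Phase II SAP 17.3 has none.

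**The concern.** A relative cut with no floor treats very different subjects alike. In a tumour that produces AFP, a fall of more than 20% may reflect drug effect. In a subject whose AFP is normal at baseline, a change of 1 or 2 units can pass the cut, while a value already at the assay floor cannot fall any further. The first error raises the rate and the second lowers it, so a reader of the single rate cannot tell which dominates.

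This rate serves the biochemical-response objective. As planned, it depends partly on how many subjects happened to enrol with uninformative AFP.

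The documents handle comparable measures differently. In Phase II SAP 16.4.2, best change in target-lesion size is limited to subjects with a measurable tumour at baseline and a later assessment. The RECIST text in Protocol Appendix J asks for marker normalisation only where the marker started above normal.

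**Working it through.** **The plan's own figure.** The only design calculation concerns the primary endpoint. The inputs are a null rate of 15% ("the rate of MET+ subjects without progression at 12 weeks was assumed to be ~15% based on historical data", Phase II SAP section 7), an alternative of 30% ("It is expected that MSC2156119J treatment will lead to 30% MET+ subjects without progression at 12 weeks"), one-sided 5% alpha, 80% power, n = 48 and success at 12 or more. Exact binomial: P(X ≥ 12 | 48, 0.15) = 0.0478 and P(X ≥ 12 | 48, 0.30) = 0.8186. No smaller n meets both limits, so the figure reproduces. It does not involve AFP. The documents state no expected rate for AFP response.

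**Assumptions.** The documents give no share of low-AFP subjects, upper limit of normal, detection limit or AFP variability. The values below are assumed: low-AFP share f = 20% to 50%, and within-subject CV 10% to 20%, with 30% in one case.

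**Composition of the rate.** Reported rate = (1 − f) × p_raised + f × p_low.

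**Dilution (p_low = 0).** With p_raised = 30%, the rate is 0.8 × 30 = 24.0% at f = 20% and 0.5 × 30 = 15.0% at f = 50%. In whole subjects, with exact 90% CIs:

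| Assumed | All treated | Raised AFP only |
|---|---|---|
| f = 20%, p_raised = 30% | 11/48 = 22.9% (13.4–35.1) | 11/38 = 28.9% (17.2–43.3) |
| f = 40%, p_raised = 40% | 12/48 = 25.0% (15.1–37.3) | 12/29 = 41.4% (25.9–58.3) |

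**Small absolute changes (p_low > 0).** A move from 5 to 3.9 is a fall of 1 − 3.9/5 = 22% and counts as a response. For two independent log-normal readings with the same true value, P(fall > 20%) = Φ(ln 0.8 / (√2 σ)), with σ = √ln(1 + CV²). This gives 5.7%, 14.5% and 21.3% at CV 10%, 15% and 20%. With p_low running from 0 to 21.3%, the reported rate is:
- p_raised = 30%: 24.0% to 28.3% at f = 20%, and 15.0% to 25.6% at f = 50%.
- p_raised = 10%: 8.0% to 12.3% at f = 20%, and 5.0% to 15.6% at f = 50%.

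So the reported rate can lie below or above the rate in subjects with raised AFP. For example, take f = 40%, p_raised = 20% and CV 30% (p_low about 30%, or 6 of 19). The all-treated rate is then (6 + 6)/48 = 25.0% (15.1–37.3), against 6/29 = 20.7% (9.4–36.8) in the raised group. For scale, the standard error at 30% and n = 48 is √(0.3 × 0.7/48) = 6.6 points.

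**Values at the floor (Phase Ib rule).** A baseline of 1.1 times the detection limit followed by a reading below it scores as 1 − 0.5/1.1 = 54.5%, a response. Below the limit both times scores as 0%, a certain non-response. In Phase II both cases are undefined.

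**The case against.** The strongest reply is that little is hidden. The line plot separates subjects by baseline AFP, the listing flags each responder, laboratory listings carry normal ranges, and baseline AFP at 200 IU/mL is tabulated. A diligent reader could recount the rate. Phase II SAP 10.2 also says that subgroup analyses may cover some secondary endpoints. This stands to the extent that the individual data will be visible. But these displays give no rate, denominator or interval, and 16.3 does not take up AFP response.

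The noise calculation is also open to attack. It uses a constant CV, so the chance of a spurious fall is the same at AFP 5 and at AFP 5000, yet noise is added only to the low group. It shows that a 20% cut can be crossed by chance. It does not show that low-AFP subjects are noisier, or that restricting the analysis removes noise. At f = 20% the largest shift from the p_raised values of 10% and 30% is 6 points, below the 6.6-point standard error. These objections stand.

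Finally, the protocol defines the rate over subjects without restriction and places efficacy on the ITT/safety set. The Phase II SAP postdates an administrative interim efficacy analysis. Making the group at or above 200 IU/mL the headline would depart further from the protocol and drop raised values below 200. That objection stands too, and the fix below respects it.

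**Conclusion.** The point holds as a reporting gap in a descriptive secondary endpoint. The all-treated rate mixes subjects in whom AFP can inform about drug effect with subjects in whom it largely cannot, and no planned table separates them. The size and direction cannot be derived from the documents. The figures above are illustrations under assumed low-AFP shares and CVs.

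A reader might infer more than the documents support:
- That low-AFP subjects cannot be scored at all. A percent change is calculable for any measurable value; the difficulty is interpretation.
- That any fall at any time counts. One time point is scored.
- That the group below 200 IU/mL is the normal-AFP group. It can include raised values.
- That the half-limit rule distorts the Phase II rate. It appears only in the Phase Ib SAP.
- That the trial's main conclusion is at risk. The primary test, n = 48 and the threshold of 12 do not use AFP.

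**What to change.** In Phase II SAP 16.2.7:
1. Keep the protocol-defined all-treated rate.
2. Add a prespecified AFP response rate among subjects with raised baseline AFP, meaning above the laboratory's upper limit of normal. Also give the rate by the existing 200 IU/mL split. Each has its own denominator and exact 90% CI.
3. State that biochemical activity will be interpreted from the raised group.
4. State one rule for AFP values below the detection limit, covering baseline and later readings.

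In Phase Ib SAP 16.2.1.6, add the raised-AFP row overall only. With at most 18 subjects already split by dose and c-Met status, finer cells would be too small to read.

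The data are already collected, so the cost is a few lines of wording and a few extra table rows. The statistical price is a smaller denominator and a wider interval. In the 40% example the width goes from 37.3 − 15.1 = 22.2 points on 48 subjects to 58.3 − 25.9 = 32.4 points on 29.
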